#### Superiority

The hypotheses to be tested for superiority of the test and reference products over Vehicle are:

$$H_0: p_T \leq p_V \text{ versus } H_A: p_T > p_V$$

$$H_0: p_R \leq p_V \text{ versus } H_A: p_R > p_V$$

Where  $p_T$ ,  $p_R$  and  $p_V$  are the proportions of subjects with clinical cure at Visit 4/Follow-up for the test, reference and Vehicle products, respectively. The tests will be conducted independently for the test product vs. vehicle and the reference product vs. vehicle using two-sided,  $\alpha = 0.05$ ,

continuity-corrected Z-tests. Superiority will be established if the proportion of subjects with clinical cure in the active treatment group is greater than and statistically different ( $p < 0.05$ ) from that in the Vehicle. Rejection of the null hypothesis supports the conclusion of superiority of the test and reference products over the Vehicle product for the primary efficacy variable.

The analyses in the mITT population will be considered definitive and those in the PP population as supportive.

Analysis for superiority (continuity-corrected p-value for treatment comparison) will be performed based on the following SAS code (SAS Institute v.9.4) e.g. trt=2 for Reference vs. trt=3 for Vehicle:

```
proc freq data=XX ;  
  where trt in (2,3);  
  table trt * cure /chisq ;  
  run;
```

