Each investigational site where study medication is dispensed to at least one subject will be required to randomly select one block of study medication [REDACTED] to be maintained as retain samples. The investigator will maintain one randomly selected block of study medication from each shipment of study medication received. As per the Code of Federal Regulations Part 21, Section 320.38(e), "Each reserve sample shall be stored under conditions consistent with product labeling and in an area segregated from the area where testing is conducted and with access limited to authorized personnel (stored between 20° to 25°C (68° to 77°F).; even after the study has concluded. Each reserve sample shall be retained for a period of at least five (5) years following the date on which the application or supplemental application is approved, or, if such application or supplemental application is not approved, at least five (5) years following the date of completion of the bioavailability study in which the sample from which the reserve sample was obtained or was used." The investigator will store the retain sample study medication until such time as written notification is received from Perrigo that the samples are no longer required.

Storage and Test Article Accountability

Study articles used to conduct this study will be maintained under adequate security by the investigator or designee. Each investigator site will ensure that the temperature of study medication is monitored and recorded throughout the study. The study medication should be stored between 20° to 25°C (68° to 77°F) and should not be frozen, as recommended in the labeling for Mupirocin Cream USP, 2%. The medication should be kept away from children unless the subject is a child. The investigator will not supply study medication to any person not enrolled in this study, or to any physician or scientist except those named as sub-investigators.

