The primary efficacy endpoint is the proportion of subjects in each treatment group with clinical cure, defined as a SIRS score of 0 for all signs and symptoms at Visit 4/Follow-up (7 days after the end of treatment). Secondary efficacy endpoints are the proportion of subjects with clinical cure at Visit 3/End of Treatment, bacteriological cure (defined as elimination of *S. aureus* and *S. pyogenes* or response was such that no culture material was available and therefore evidence of pathogen eradication) at Visit 3/End of Treatment, and bacteriological cure at Visit 4/Follow-up.

Equivalent efficacy

The clinical equivalence of the test and reference treatments will be based on the proportions of subjects with clinical cure at Visit 4/Day 17 (Follow-up, 7 days after end of treatment).

The hypothesis tested for clinical equivalence between test and reference will be:

$H_0: p_T - p_R < -0.20$ or $p_T - p_R > 0.20$ versus

$$H_A: -0.20 \leq p_T - p_R \leq 0.20.$$

Where p_T and p_R were the proportions of subjects with clinical cure at Visit 4/Day 17 for the Test and Reference products, respectively. The Test product would be considered to be clinically equivalent to the Reference product if the 90% confidence interval (CI) of the difference between their proportions of subjects with clinical cure, calculated by the Wald's method with Yates' continuity correction, is contained within the limits -20.0% to +20.0%. Rejection of the null hypothesis would support the conclusion of therapeutic equivalence between the Test and Reference products for the primary efficacy variable.

Analysis in the PP population will be considered definitive and those in the mITT population will be considered supportive.

Superiority

The test of superiority of each active treatment over vehicle will be based on the proportions of subjects in each treatment group with clinical cure at the Visit 4/Day 17 [REDACTED]

Protocol No: PRG-NY-19-002

The hypotheses tested for superiority of the test and reference products over Vehicle will be:

$H_0: p_T \leq p_V$ versus $H_A: p_T > p_V$

$H_0: p_R \leq p_V$ versus $H_A: p_R > p_V$

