Where p_T , p_R , and p_V are the proportions of subjects with clinical cure at the Visit 4/Day 17 for the Test, Reference, and Vehicle products, respectively. The tests will be conducted independently for the Test product and the Reference product using two-sided, $\alpha = 0.05$, continuity-corrected Z-tests. Superiority would be established if the proportion of subjects with clinical cure at the Visit 4/Day17 in the active treatment group is significantly greater ($p < 0.05$) than that in the Vehicle group. Rejection of the null hypothesis would support the conclusion of superiority of the Test and Reference products over the Vehicle for the primary efficacy variable.

Superiority analyses in the mITT population will be considered definitive and those in the PP population will be considered supportive.

The same tests/methods, including the missing data imputation methods, as for the primary analyses will be conducted for the secondary analyses.

Safety and Adverse Events Analysis

The frequency and percent of subjects with adverse events will be summarized by MedDRA system organ class and preferred term and by severity and relationship to study drug for all three treatment groups. [REDACTED]

[REDACTED]. The comparable safety of the Test and Reference treatments will be evaluated by statistical comparison of the proportion of subjects who reported any adverse events. Safety comparisons will be performed on the ITT (safety) population.

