## 5 Planned Analyses

### 5.1 Methodological Considerations

Tables will have columns corresponding to or be stratified by the treatment groups.

All data will be listed by treatment group, subject and visit/time point where appropriate. The total number of subjects under the stated population (N) will be displayed in the header of summary tables. Efficacy data will be tabulated by site and if obviously inconsistent discrepancies will be observed with the results across all sites, then these differences will be explored and addressed in the final study report.

Data will be summarized using descriptive statistics for continuous variables. Unless otherwise specified, descriptive statistics will include number of subjects, mean, standard deviation, minimum, median and maximum. The statistic “Missing” will also be presented as the number of missing entries/subjects, if any at that visit/timepoint, and presented as a summary statistic only when non-zero. The minimum and maximum statistics will be presented to the same number of decimal places as the original data. The mean and median will be presented to one more decimal place than the original data, whereas the standard deviation will be presented to two more decimal places than the original data.

Categorical variables will be summarized by frequency (n) and percentage (%). Percentage will be obtained as  $(n/N) * 100$ . Unless otherwise stated, all percentages will be expressed to one decimal place.

Study days will be calculated as follows:

- For events or findings on or after the date of the first study treatment:
  - o Study Day = Date of the event or finding – Date of the first treatment + 1

- For events or findings prior to the date of the first study treatment:
  - o Study Day = Date of the event or finding – Date of the first treatment
- All dates will be displayed in DDMMYY format.

Two-sided hypothesis testing will be conducted for all the tests. P-values less than 0.05 will be considered statistically significant. No adjustments of p-values for multiple comparisons will be made. No interim analyses are planned.

All statistical analysis will be conducted using SAS® version 9.4 or higher (SAS® Institute, Cary, North Carolina).

[REDACTED]

[REDACTED]

[REDACTED]

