### **5.3 Demographics and Baseline Characteristics**

Baseline variables (e.g., sex, age, ethnic origin) will be summarized descriptively by treatment group. Any significant baseline differences will be reviewed for their potential impact on the efficacy findings.

Continuous variable at baseline will be examined by two-way analysis of variance (ANOVA) with treatment and site as fixed effects when normal error and homogeneous variance assumptions are satisfied, or by non-parametric rank-based ANOVA when they are not, to compare treatment group differences. The summary tables will include the mean, standard deviation, minimum and maximum. For each categorical variable, the summary will include frequencies and percentages and be examined by Cochran-Mantel-Haenszel test and stratified by site.

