#### Equivalent Efficacy

The compound hypothesis to be tested for clinical equivalence between test and reference is:

$$H_0: p_T - p_R < -0.20 \text{ or } p_T - p_R > 0.20 \text{ versus}$$

$$H_A: -0.20 \leq p_T - p_R \leq 0.20.$$

Where  $p_T$  and  $p_R$  are the proportions of subjects with clinical cure at Visit 4/Follow-up for the test and reference products, respectively. The test product will be considered to be therapeutically equivalent to the reference product if the 90% CI on the difference in their proportions of subjects with clinical cure, calculated by Wald's method with Yates' continuity correction, is contained within the limits -0.20 to +0.20. Rejection of the null hypothesis supports the conclusion of therapeutic equivalence between the test and reference products for the primary efficacy variable.

The result of the analysis in the PP population will be considered definitive and that in the mITT population as supportive.

Analysis for therapeutic equivalence (i.e. 90% confidence interval) will be performed based on the following SAS code (SAS Institute v.9.4) e.g. trt=1 for Test and trt=2 for Reference:

```
proc freq data=XX;
  where trt in (1,2);
  tables trt*cure /alpha=0.10 riskdiff (CORRECT CL=(WALD));
run;
```

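### Should the definitive efficacy analyses drop the continuity correction and stratify by site?

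*SAP*

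**What the plan says.** Protocol 8.1 and SAP 5.7.1 agree on the method.

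- **Equivalence (per-protocol population definitive).** A 90% interval for test minus reference, "calculated by the Wald's method with Yates' continuity correction", must lie within ±0.20. The SAP code is "tables trt*cure /alpha=0.10 riskdiff (CORRECT CL=(WALD".
- **Superiority over vehicle (mITT population definitive).** The protocol names "continuity-corrected Z-tests" at a two-sided 0.05 level. The SAP repeats this: "Analysis for superiority (continuity-corrected p-value for treatment comparison) will be performed based on the following SAS code". The code is "table trt * cure /chisq", and the sentence before it makes clear that the corrected p-value is the one to report.
- **Site.** Neither code block contains a site variable. In the visible text, site enters efficacy only in SAP 5.1: "Efficacy data will be tabulated by site", with marked inconsistencies to be explored in the report. For baseline variables SAP 5.3 goes further: categorical ones are "examined by Cochran-Mantel-Haenszel test and stratified by site", and continuous ones are compared with site as a fixed effect.
- **Blocking.** Protocol 6.2 describes block randomization but does not say in the visible text whether blocks are assigned within site. The retention rule suggests that kits reach sites in whole blocks: "Each investigational site where study medication is dispensed to at least one subject will be required to randomly select one block of study medication".

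**The concern.** A continuity correction makes an approximate test stricter than its stated level and makes an interval wider than its label. If blocks are filled within site and cure rates differ between sites, leaving site out has a similar effect, because the pooled variance then includes between-site variation that the balanced comparison does not carry. It also looks odd that the SAP accounts for site in baseline tables, where nothing is decided, and not in the analyses that decide the trial.

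At stake is efficiency, not a false claim. Conservatism costs power, or extra subjects for the same power, on the equivalence comparison and on both superiority comparisons. The cost grows as arms shrink, and culture-negative subjects leave the mITT and per-protocol populations after randomization.

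**Working it through.** **Inputs.** From the documents: the ±0.20 margin, the 90% interval, the two-sided 0.05 level (0.025 in the favourable direction) and the two corrected methods. Assumed, because the documents redact or do not show them: arm sizes, a vehicle arm half the size of each active arm, cure rates and the spread between sites. No stated power or sample size is visible, so there is no plan figure to reproduce.

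**1. Size of the correction.** The term is c = ½(1/n₁ + 1/n₂).

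- Equivalence, 150 per arm, cure 0.70 in both: the uncorrected half-width is 1.645 × √(2 × 0.70 × 0.30/150) = 1.645 × 0.0529 = 0.0870. The correction adds 1/150 = 0.0067, giving 0.0937.
- Superiority, 200:100, common cure 0.60: SE = √(0.24 × (1/200 + 1/100)) = 0.060 and c = 0.0075. The effective critical value is 1.96 + 0.0075/0.060 = 2.085, a level of about 1.9% instead of 2.5%.

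**2. Exact superiority results** (binomial enumeration, cure 0.70 v 0.50; losses taken before rounding).

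| Active:vehicle | Planned power | Uncorrected | Loss (points) |
|---|---|---|---|
| 60:30 | 38.0% | 46.9% | 8.9 |
| 100:50 | 60.7% | 66.8% | 6.1 |
| 150:75 | 79.6% | 83.2% | 3.5 |
| 200:100 | 90.3% | 92.2% | 1.9 |

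Over common cure rates from 0.3 to 0.9, the planned level in the favourable direction is 1.1 to 1.9%. The uncorrected level is about 2.3 to 2.9% and exceeds 2.5% in 20 of 28 cells. The largest loss found with planned power near 80% is 6.6 points (100:50, 0.90 v 0.70: 79.8% v 86.4%).

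**3. Exact equivalence results** (true cure 0.70 in both arms).

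| Per arm | Planned power | Uncorrected | Loss (points) |
|---|---|---|---|
| 100 | 80.8% | 85.4% | 4.5 |
| 150 | 95.6% | 96.8% | 1.2 |
| 200 | 99.1% | 99.4% | 0.3 |

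**4. The same cost in subjects.** For 0.70 v 0.50 at 2:1 and 80% power, the usual two-proportion formula gives 69 vehicle subjects without the correction and 77 with it. Active plus vehicle, that is 3 × 69 = 207 against 3 × 77 = 231, or 24/207 = 12% more. Over other assumed rates, at 80 to 90% power, the range is about 8 to 18%.

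**5. What leaving out site adds.** With balance within site, the pooled variance p̄(1 − p̄) exceeds the relevant variance by Var(p_site). For a mean cure of 0.60 and a between-site SD of 0.15, the excess is 0.0225/0.24 = 9.4%. The effective critical value is 1.96/√(1 − 0.094) = 2.06, a level of about 2.0%. So at 200:100 even this spread matters slightly less than the correction. In simulation, leaving out site became the larger cause only at an SD of 0.19, for superiority, and not at 100:50.

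In trials simulated with unequal sites, blocks within site and small sites pooled, stratifying by itself changed superiority power by:

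- −2.9 to −0.1 points at site SD 0 (logit scale);
- −2.2 to +1.2 points at SD 0.5;
- +1.1 to +4.7 points at SD 1.

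**6. What the alternatives cost.** Probability of declaring equivalence when true cure rates are 0.95 and 0.75, at the margin (nominal 5%):

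| Per arm | Planned | Correction dropped |
|---|---|---|
| 60 | 3.7% | 5.7% |
| 100 | 3.7% | 6.0% |
| 150 | 3.9% | 5.6% |
| 200 | 4.0% | 5.5% |

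A site-stratified Mantel-Haenszel interval with Sato variance gave 4.3 to 5.2% when the difference was the same at every site. When the difference varied between sites it gave 4.6 to 6.5%, against 2.6 to 4.0% for the planned interval. The simulation standard error is √(0.05 × 0.95/10,000) = 0.22 points, so 6.5% is not noise.

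**The case for a change.** The best case for changing the plan is that the conservatism is certain in direction and avoidable without new data. The planned methods were conservative in every case computed. A site-stratified Cochran-Mantel-Haenszel test without the correction had more superiority power than the planned test in all 24 simulated scenarios, by 1.8 to 12.8 points. The SAP could still be amended before unblinding.

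The direction stands. The rest is weaker than it looks.

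- Dropping the correction supplies 1.6 to 9.3 of those points, and the top of the range comes from small, underpowered designs. Stratifying is a separate decision, and it pays only if sites differ widely. Nothing in the documents suggests that they do.
- Balance within site is inferred from how kits are handled. If blocks are not within site, the argument for stratifying falls away.
- The gain is bought with error control. For an equivalence claim, false equivalence is the error to guard against, and both alternatives can exceed 5%.
- If the redacted sample size already allows for the correction, no power is lost against plan and the extra subjects are already budgeted.
- Protocol section 16 cites a draft product guidance that was not available here. Whether it prescribes the corrected method is unknown, which is a further reason not to replace the method on this evidence.

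The contrast with the baseline tables is not a contradiction. Those comparisons are descriptive support, and SAP 5.1 already provides for a look at efficacy by site.

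**Conclusion.** The description is accurate, but no change to the plan follows. The planned analyses are valid, prespecified, identical in protocol and SAP, and they keep error rates below nominal. The price, with assumed arm sizes and cure rates and planned power of about 80% or more, runs from almost nothing to about 7 points of power. It is typically 2 to 4 points for superiority at 150:75 to 200:100, and about 1 point or less for equivalence from 150 per arm. The size in this trial cannot be determined from the public copy.

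Keeping the correction is a defensible choice when the definitive claim is equivalence. Leaving site out costs little unless the between-site SD of the cure probability exceeds about 0.15, and it is conservative only if arms are roughly balanced within site. A site-stratified analysis could be reported as supportive, but no conclusion of the plan depends on it.

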### 5.7.2 Secondary Endpoints

Secondary efficacy endpoints are:

- the proportion of subjects with clinical cure at Visit 3/End of Treatment;
- the proportion of subjects with bacteriological cure (defined as elimination of *S. aureus* and *S. pyogenes* or response was such that no culture material was available and therefore evidence of pathogen eradication) at Visit 3/End of Treatment;
- the proportion of subjects with bacteriological cure at Visit 4/Follow-up.

The same tests/methods, including the missing data imputation methods, as for the primary analyses will be conducted for the secondary analyses.

### 5.8 Safety Variables and Analyses

All safety data will be listed and tabulated. The analysis will be performed on the safety/ITT population. Safety parameters include adverse events, vital signs and concomitant medications.

#### Adverse Events

Adverse events (AEs) will be coded in MedDRA, version 22.0. Treatment-Emergent Adverse Event (TEAE) is defined as any AE occurs on or after application of the first dose of study drug. Number and percent of subjects reporting TEAEs will be tabulated by treatment group. Summary of TEAEs will be presented by body system and preferred term for the ITT population, and further by severity and relationship to study medication. Most common TEAEs will include those reported by 5% or more subjects for any treatment group will be summarized by preferred term. In the summaries of incidence rates (frequencies and percentages), severity and relationship to study drug, subjects who report more than one event that are mapped to the same preferred term will be counted only once under the strongest severity and relationship, accordingly. The difference between Test and Reference treatments with regard to severity and

frequency of their dermatological adverse events will be statistically evaluated using Chi-Square or Fisher's exact test to compare the proportions of subjects of the two active treatment groups who report any TEAE.

Treatment-Emergent Serious Adverse Events (TESAEs) will be discussed within the clinical study report. TEAEs, TESAEs and TEAEs that led to treatment interruption temporarily or treatment discontinued permanently will be presented in data listings.

#### Concomitant Medications and Vitals Signs

Concomitant medications will be coded using the WHO Drug Dictionary, version March 2019, and will be presented in data listings. All vital signs data will be displayed in listings.

## **6 Appendices**

### **6.1 Handling of Missing or Incomplete Dates for Adverse Events and Concomitant Medications**

#### Adverse Events

Handling of partial dates is only considered for the start date. An adverse event with a partial start date is considered treatment emergent if:

- only the day is missing and the start month/year is the same or after the month/year of the first dose
- the day and month are missing and the start year is the same or greater than the year of the first dose date
- the start date is completely missing

#### Concomitant Medications

Handling of partial dates is only considered for the stop date. A medication with a partial stop date is considered concomitant if:

- only the day is missing and the stop month/year is the same or after the month/year of the first dose
- the day and month are missing and the stop year is the same or greater than the year of the first dose date
- the stop date is completely missing or the medication is ongoing

### **6.2 Summary of Assessments**

The schedule of visits and procedures to be conducted at each visit are summarized in the Schedule of Study Procedures.

A 2D grid of black and white blocks. The pattern consists of several L-shaped and T-shaped structures. The L-shaped structures are located in the top-left, top-right, and middle-left columns. The T-shaped structures are located in the top-right, middle-right, and bottom-right columns. The remaining cells are white. The grid is composed of 16 rows and 8 columns.
